8.4.2.2. Summaries of Laboratory Abnormalities

The following summaries (number and percentage of subjects) for treatment-emergent laboratory abnormalities will be provided by lab test; subjects will be categorized according to most severe postbaseline abnormality grade for a given lab test:

- Treatment-emergent laboratory abnormalities
- Treatment-emergent Grade 3 or 4 laboratory abnormalities

For all summaries of E/C/F/TAF laboratory abnormalities, the denominator is the number of subjects with any nonmissing postbaseline values up to 30 days after the last E/C/F/TAF dose date for subjects who do not participate in the B/F/TAF OL extension phase or up to the date of the first B/F/TAF study drug dose for subjects who participate in the B/F/TAF OL extension phase.

For all summaries of B/F/TAF laboratory abnormalities, the denominator is the number of subjects with any nonmissing postbaseline values up to 30 days after the last B/F/TAF dose date.

By-subject listings of treatment-emergent graded abnormalities and Grade 3 or 4 laboratory abnormalities will be provided by subject ID number and visit in chronological order.

8.4.3. Metabolic Laboratory Evaluations

For metabolic assessments, including fasting glucose and the lipid panel (ie, total cholesterol, triglycerides, LDL, HDL, total cholesterol to HDL ratio), only those measurements under fasting status will be summarized.

Fasting lipid data will also be analyzed by using the following National Cholesterol Education Program (NCEP) ATP III categories {[National Cholesterol Education Program \(NCEP\) 2001](#)}:

- For total cholesterol (mg/dL): < 200, 200-239, \geq 240
- For LDL (mg/dL): <100, 100-129, 130-159, 160-189, and \geq 190
- For HDL (mg/dL): < 40, \geq 40 to < 60, and \geq 60
- For triglycerides (mg/dL): < 150, 150-199, 200-499, and \geq 500

The number and proportion of subjects for the above categories of each lipid parameter will be summarized by its baseline category at Weeks 24, 48, 72, and 96 for the E/C/F/TAF Safety Analysis Set and at Weeks 24 and 48 for the B/F/TAF Safety Analysis Set.

In addition, the number and proportion of subjects in the E/C/F/TAF Safety Analysis Set who took lipid modifying medication at study entry and initiated medication during the E/C/F/TAF phase and the number and proportion of subjects in the B/F/TAF Safety Analysis Set who took lipid modifying medication at the start of the B/F/TAF OL extension phase and initiated medication during the B/F/TAF OL extension phase will be provided.

A lipid modifying medication is defined as a medication with drug class (Anatomical Therapeutic Chemical drug class Level 2) “LIPID MODIFYING AGENTS” and CMDECOD containing the wording of “STATIN”.

A sensitivity analysis of fasting lipid tests (including total cholesterol, LDL, HDL, triglycerides, and total cholesterol to HDL ratio) will be performed using the E/C/F/TAF Safety Analysis Set by excluding subjects who took lipid modifying medication at study entry or initiated lipid modifying medication during the study prior to Week 96: baseline, postbaseline, and changes from baseline at Week 96 will be summarized. Only subjects with both baseline and Week 96 postbaseline values will be included in the analysis.

A sensitivity analysis of fasting lipid tests (including total cholesterol, LDL, HDL, triglycerides, and total cholesterol to HDL ratio) will be performed using the B/F/TAF Safety Analysis Set by excluding subjects who took lipid modifying medication at the start of the B/F/TAF OL extension phase or initiated lipid modifying medication during the B/F/TAF OL extension phase: baseline, postbaseline, and changes from baseline at Weeks 24 and 48 will be summarized. Only subjects with both baseline and Week 48 postbaseline values will be included in the analysis.

Median (Q1, Q3) of change from baseline in fasting metabolic assessments over time will be plotted.

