	Magnesium	Decrease	Magnesium (Hypomagnesemia)
	Phosphate	Decrease	Phosphate (Hypophosphatemia)
	Serum Glucose (Fasting)	Increase	Serum Glucose (Fasting, Hyperglycemia)

Battery	Lab Test Label Used in l-labtox Listing	Toxicity Direction	Lab Test Label Used in t-labtox Table
	Serum Glucose (Fasting)	Decrease	Serum Glucose (Fasting, Hypoglycemia)
	Serum Glucose (Nonfasting)	Increase	Serum Glucose (Nonfasting, Hyperglycemia)
	Serum Glucose (Nonfasting)	Decrease	Serum Glucose (Nonfasting, Hypoglycemia)
	Serum Potassium	Increase	Serum Potassium (Hyperkalemia)
	Serum Potassium	Decrease	Serum Potassium (Hypokalemia)
	Serum Sodium	Increase	Serum Sodium (Hypernatremia)
	Serum Sodium	Decrease	Serum Sodium (Hyponatremia)
	Total Bilirubin	Increase	Total Bilirubin (Hyperbilirubinemia)
	Total Cholesterol (Fasting)	Increase	Total Cholesterol (Fasting, Hypercholesterolemia)
	Triglycerides (Fasting)	Increase	Triglycerides (Fasting, Increased)
	LDL (Fasting)	Increase	LDL (Fasting, Increased)
	Urea Nitrogen (BUN)	Increase	Urea Nitrogen (Increased)
	Uric Acid	Increase	Uric Acid (Hyperuricemia)
	Uric Acid	Decrease	Uric Acid (Hypouricemia)

20) Concomitant nonstudy-drug ARV medications (ie, ARV medications other than study drug that are taken while receiving study drug) will be flagged in “Nonstudy-Drug Antiviral Medication” listing. The logic to define concomitant nonstudy-drug ARV is similar to concomitant non-ARV Medications (see details in Section 8.6.2)

21) Lipid modifying medication analyses:

- Lipid modifying medication is defined to be the concomitant medication with ACLAS “LIPID MODIFYING AGENTS” and CMDECOD contains wording of “STATIN” in the ADCM dataset.
- Subjects who took lipid modifying medications at study entry refer to the subjects who have any use of the lipid modifying agents at study day 1 (ie, the first E/C/F/TAF dose date).
 - a) More specifically, subjects with “Lipid Modifying Agent Use at Study Entry” include those subjects in E/C/F/TAF Safety Analysis set meeting both the following criteria:
 - 1) any selected CM record with the start date \leq the first E/C/F/TAF dose date, and
 - 2) the end date of the selected CM record \geq the first E/C/F/TAF dose date or the end date of the selected CM record is ongoing

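### The SAP's rule for lipid modifying medication captures statins only, so a subject taking solely a non-statin lipid agent would be counted as a non-user and kept in the sensitivity analyses meant to exclude users

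*SAP*

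**What the plan says.** SAP 8.4.3 sets two conditions. The first is the class: "A lipid modifying medication is defined as a medication with drug class (Anatomical Therapeutic Chemical drug class Level 2"). The class it names is LIPID MODIFYING AGENTS. The second concerns the coded drug name, "and CMDECOD containing the wording of", with STATIN as the required string. Appendix 7 item 21 gives the programmers the same rule. It opens with "Lipid modifying medication is defined to be the concomitant medication with ACLAS", names that same class, and then adds the name condition, "and CMDECOD contains wording of", again with STATIN as the string. Both conditions must hold. Neither section gives a reason for the second one, and neither labels the resulting outputs as statin use.

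The definition has two uses in SAP 8.4.3:

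- **User counts.** The number and proportion of subjects "who took lipid modifying medication at study entry and initiated medication during the E/C/F/TAF phase" are reported, with a matching count for the B/F/TAF extension.
- **Sensitivity analyses.** "A sensitivity analysis of fasting lipid tests (including total cholesterol, LDL, HDL, triglycerides, and total cholesterol to HDL ratio) will be performed". For the E/C/F/TAF phase, the exclusion is worded as follows: "excluding subjects who took lipid modifying medication at study entry or initiated lipid modifying medication during the study prior to Week 96". The extension has its own version, with the exclusion worded "excluding subjects who took lipid modifying medication at the start of the B/F/TAF OL extension phase or initiated lipid modifying medication during the" (the extension phase). The E/C/F/TAF analysis also requires both a baseline and a Week 96 value; the extension analysis requires baseline and Week 48.

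Separately, SAP 8.6.2 summarises all non-ARV concomitant medications by preferred name in each phase and lists the subjects who took them.

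**The concern.** The label covers a whole drug class, but the rule covers only the part of that class whose coded name contains one string. A reader of the tables would take the count to be everyone on lipid therapy, and the sensitivity analysis to be free of lipid drugs. Neither would be true if any subject takes only a non-statin agent.

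Lipids are a live safety question in this programme: Protocol 1.2.5 reports increases in fasting total cholesterol, LDL and triglycerides with E/C/F/TAF in the pooled treatment-naive trials. The purpose of setting aside subjects on lipid drugs is to see lipid changes without their effect. Because the analysis includes triglycerides and HDL, and not only cholesterol and LDL, a statin-only exclusion does not obviously serve all of its parameters.

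**Working it through.** The plan states no figure on this point, so there is none to reproduce. The check is on the logic of the rule, followed by a scale calculation.

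**Logic.** Write C for membership of the ATC class and S for the string STATIN in the coded name. The SAP rule is C and S; the label implies C.

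| Subject's medication | C | C and S | Counted as user | In sensitivity set |
|---|---|---|---|---|
| No lipid agent | no | no | no | yes |
| Statin, or combination whose coded name contains STATIN | yes | yes | yes | no |
| Statin plus a separate non-statin agent | yes | yes | yes | no |
| Non-statin agent(s) in the class only | yes | **no** | **no** | **yes** |
| Drug outside the class with STATIN in its name | no | no | no | yes |

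Only the fourth row differs between rule and label. The last row shows that S is not needed to screen out unrelated drugs, because C already does that. Within the class, S can only remove agents.

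**Scale.** The E/C/F/TAF Safety Analysis Set has 55 subjects (mock disposition table, SAP Appendix 6). One missed subject is 1/55 = 1.8 percentage points of the user count.

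The sensitivity set is smaller, but the documents give neither the number of statin users (s) nor the number on non-statin agents only (k). The values below are assumptions, chosen only to show the range. Missing Week 96 values are ignored.

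- Retained under the SAP rule = 55 − s
- Retained under class alone = 55 − s − k
- Share of the retained set on a lipid agent = k/(55 − s)
- Reported user proportion = s/55 under the SAP rule, (s + k)/55 under class alone

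| s | k | Retained, SAP rule | Retained, class alone | Share on a lipid agent | User proportion: SAP rule, class alone |
|---|---|---|---|---|---|
| 15 | 0 | 40 | 40 | 0% | 27.3%, 27.3% |
| 15 | 1 | 40 | 39 | 2.5% | 27.3%, 29.1% |
| 15 | 3 | 40 | 37 | 7.5% | 27.3%, 32.7% |
| 15 | 5 | 40 | 35 | 12.5% | 27.3%, 36.4% |
| 25 | 0 | 30 | 30 | 0% | 45.5%, 45.5% |
| 25 | 1 | 30 | 29 | 3.3% | 45.5%, 47.3% |
| 25 | 3 | 30 | 27 | 10.0% | 45.5%, 50.9% |
| 25 | 5 | 30 | 25 | 16.7% | 45.5%, 54.5% |

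**Direction.** The analysis summarises baseline, post-baseline and change. A subject on the same non-statin agent throughout is treated at both time points, so the drug mainly shifts the absolute values. A subject who starts one on study is treated only at the later time point, and the drug effect enters the change, where it could mask a rise. Stopping such an agent on study could exaggerate a rise.

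**The case against.** The strongest case against acting has four parts.

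1. **Nobody may be affected.** No section reports a subject on a non-statin lipid agent. This stands: every consequence is conditional. Protocol Tables 4-1 and 5-1 disallow two statins and attach a caution to a third during E/C/F/TAF, which makes non-statin use plausible but does not show that it occurred.
2. **Subjects who also take a statin are still caught.** This stands for the exclusion, because item 21 tests for any qualifying medication record. One wrinkle remains in the counts: a subject on a non-statin agent at entry who adds a statin on study would be classed as an initiator rather than as a user at entry.
3. **The data are visible elsewhere.** The concomitant-medication summary and listing would show any non-statin lipid agent. That is true, but they do not feed the exclusion and would not correct the lipid outputs.
4. **A statin-only analysis is legitimate.** It is, if it is labelled so. Here the definition is narrow, the outputs carry the broad label, and no reason is given.

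A reader might also infer that the plan hides lipid increases, especially in triglycerides. The documents do not support that. The number affected is unknown, the direction for stable users is not established, and the main fasting-lipid summaries, lipid category tables and graded abnormalities do not use this definition.

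**Conclusion.** The rule and its label do not match, and the mismatch is explicit in both the SAP body and the programming specifications. Any subject whose lipid agents are all non-statins in the class would be misclassified in the user and initiator counts and wrongly retained in the sensitivity analyses of both phases.

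The actual effect is unknown and may be zero. Each such subject would move the E/C/F/TAF user count by 1.8 points. Under the assumed 15 to 25 statin users and 0 to 5 non-statin-only users, 0% to 16.7% of the retained set would be on a lipid agent; those inputs are not evidence about this trial.

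The reach is limited to supplementary descriptive safety outputs in a single-arm study with no formal testing (SAP 3.5). The primary endpoint, Grade 3 or higher adverse events up to Week 48, is untouched. This is a minor point, worth correcting because it is cheap.

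**What to change.** Delete the STATIN condition in SAP 8.4.3 and in Appendix 7 item 21, and define lipid modifying medication by the ATC Level 2 class alone. Report statins as a labelled sub-row of the user and initiator counts. Apply the same definition to the exclusion in both phases.

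The cost is one programming condition in two places, plus a note in the final clinical study report, which SAP Section 1 already requires for changes after finalisation. The downside is a sensitivity set smaller by the number of subjects on non-statin agents only.

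If a statin-only analysis is what was intended, keep the rule, rename the counts and the sensitivity analyses as statin use, and report non-statin lipid agents separately.

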1.2.5. Clinical Trials of Elvitegravir/Cobicistat/Emtricitabine/Tenofovir Alafenamide (E/C/F/TAF)

Emtricitabine and TAF have been combined with the integrase inhibitor EVG and its pharmacoenhancer COBI in the E/C/F/TAF FDC, which has been designed to be a complete treatment regimen for HIV-1 infection and is being evaluated in a broad clinical development program. The details of the key clinical studies are provided below:

- **GS-US-292-0102**, a randomized, double-blinded controlled Phase 2 study in which E/C/F/TAF is compared to Stribild® (STB), as initial treatment of HIV-infection in ART-naive patients. This is a single-variable clinical comparison of the 2 tenofovir prodrugs, TAF and TDF
- **GS-US-292-0104** and **GS-US-292-0111**, Phase 3 randomized, double-blinded studies of the safety and efficacy of E/C/F/TAF versus E/C/F/TDF in HIV-1 infected, antiretroviral treatment-naive adults. The interim Week 48 key conclusions from pooled data are as follows: 1) E/C/F/TAF once daily was noninferior to STB once daily when administered for 48 weeks to HIV-infected, ART-naive adults, as assessed using the US Food and Drug Administration (FDA)-defined snapshot algorithm with HIV-1 RNA < 50 copies/mL (E/C/F/TAF 92.4%; STB 90.4%; difference in percentages: 2.0%, 95% CI: -0.7% to 4.7%), 2) administration of E/C/F/TAF resulted in > 90% lower plasma TFV and higher intracellular TFV-DP relative to STB, 3) E/C/F/TAF showed an improved renal and bone safety profile with significantly less decline in hip and spine BMD, less increase in serum creatinine and reduction in estimated glomerular filtration rate (eGFR), 4) Increases from baseline in fasting total cholesterol fasting low density lipoprotein (LDL) cholesterol, and fasting triglycerides were noted in the E/C/F/TAF group. At Week 96 86.6% in the TAF arm and 85.2% in the TDF arm maintained HIV-RNA <50 c/mL.

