8.4.1. Summaries of Numeric Laboratory Results

Descriptive statistics will be provided for each laboratory test specified in the study protocol as follows:

- Baseline value
- Value at each postbaseline analysis window
- Change from baseline at each postbaseline analysis window

In addition, percentage change from baseline at each postbaseline analysis window will also be provided for biomarker PTH.

A baseline laboratory value for the E/C/F/TAF phase will be defined as the last nonmissing value obtained on or prior to the date of first dose of E/C/F/TAF study drug. A baseline laboratory value for the B/F/TAF OL phase will be defined as the last nonmissing value obtained on or prior to the date of first dose of B/F/TAF study drug. Change from baseline to a postbaseline visit will be defined as the postbaseline value minus the baseline value. The mean, median, Q1, Q3, minimum, and maximum values will be displayed to the reported number of digits; SD values will be displayed to the reported number of digits plus 1.

In the case of multiple values in an analysis window, data will be selected for analysis as described in Section 3.8.3.

Calcium Corrected for Albumin

Calcium corrected for albumin will be calculated and summarized. The following formula will be used when both serum calcium and albumin results for a given blood draw are available and serum albumin value is < 4.0 g/dL.

- Calcium corrected for albumin (mg/dL) = serum calcium (mg/dL) + 0.8 × (4.0 - albumin (g/dL)).

Toxicity grading for calcium will be applied based on the corrected values.

Estimated GFR

The following formula will be used to calculate eGFR_{CG}:

- eGFR_{CG} (mL/min) = $[(140 - \text{age(yrs)}) \times \text{weight (kg)} \times (0.85 \text{ if female})] / (\text{SCr (mg/dL)} \times 72)$, where weight is total body mass in kilograms, and SCr is serum creatinine.

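### The lipid sensitivity analyses drop subjects who start a statin after baseline: if on-study lipids prompt the start, this understates a rise, and the B/F/TAF rule also discards untreated values

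*SAP*

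**What the plan says.** **Main summary.** SAP 8.4.1 plans descriptive statistics that include "Change from baseline at each postbaseline analysis window". For the metabolic tests, SAP 8.4.3 adds that "only those measurements under fasting status will be summarized". Neither section sets aside values measured after a lipid drug is started, so statin-lowered values stay in.

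**E/C/F/TAF sensitivity analysis.** SAP 8.4.3 repeats the Week 96 lipid summary without subjects who were on a lipid drug at entry or who "initiated lipid modifying medication during the study prior to Week 96". It adds: "Only subjects with both baseline and Week 96 postbaseline values will be included in the analysis".

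**B/F/TAF sensitivity analysis.** The same section excludes users at the start of the extension and those who "initiated lipid modifying medication during the B/F/TAF OL extension phase". Results are for Weeks 24 and 48 OL, in subjects with baseline and Week 48 values.

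**Definitions.** A lipid modifying drug is one in that drug class whose coded name identifies it as a statin (SAP 8.4.3). In SAP Appendix 7, item 21, an initiator in either phase is a non-user at the start with a record beginning after the first dose and no later than the last dose of that phase's drug.

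**Also planned.** SAP 8.4.3 plans counts of users at entry and of initiators for both phases, and category shifts by visit. SAP 8.4.2.2 summarises the worst post-baseline grade.

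**The concern.** Protocol 1.2.5 reports that in treatment-naive adults increases in fasting total cholesterol, LDL "and fasting triglycerides were noted in the E/C/F/TAF group". A rise is therefore the direction of interest, and this single-arm study has no comparator in which a shared bias could cancel.

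The sensitivity analysis appears intended to show lipid change free of statin effect, though the SAP does not state its purpose. Excluding users at entry is a baseline restriction and raises no difficulty. Excluding later starters makes membership depend on something that happens after baseline and may be caused by the outcome. If a high or rising value leads to a prescription, the main summary hides the rise behind the treated value and the sensitivity analysis removes the subject who had it. Agreement between the two could then be read as robustness when both lean the same way.

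The B/F/TAF rule has a second fault that needs no assumption about why statins are started: it can remove a valid untreated measurement because of something that happened after it.

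**Working it through.** The plan gives no figure for this analysis, so there is none to reproduce. The number of initiators, their reasons for starting, the statin effect and the lipid SDs are not in the documents. All numerical inputs below are assumptions, for LDL in mg/dL.

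**1. Closed-form illustration.** Baseline B has mean 100 and SD 30. Untreated change D has mean +10 and SD 25, independent of B. Y = B + D. A statin is started with probability 0.40 if Y ≥ 130 and 0.03 otherwise.

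- SD(Y) = √(900 + 625) = 39.05; z = (130 − 110)/39.05 = 0.512; P(Y ≥ 130) = 0.304.
- Excluded: 0.40 × 0.304 + 0.03 × 0.696 = 14.3%.
- Slope of D on Y: 625/1525 = 0.410. E[(Y − 110); Y ≥ 130] = 39.05 × φ(0.512) = 39.05 × 0.350 = 13.66.
- Bias among those kept: −0.410 × (0.40 − 0.03) × 13.66 / (1 − 0.143) = −2.4, so the mean change is **+7.6** instead of +10.
- With a true change of 0, the same steps exclude 11.2% and give **−2.0** (simulated −1.9).
- Main summary: mean untreated LDL attributable to starters is 0.40 × 47.1 + 0.03 × 62.9 = 20.7. A 20%, 30% or 40% statin effect lowers the mean by 4.1, 6.2 or 8.3. At 30% the reported change is **+3.8**.

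The trigger here is the outcome value itself, which strengthens the selection.

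**2. Does the direction depend on why the statin is started?** A simulation of 400,000 subjects per scenario used a separate on-study trigger value. Inputs: baseline mean 100, between-subject SD 30, within-subject SD 12, SD of true change 20, true change 0 or +10, 5–20% starting, statin effect 20–40%. Bias is measured against the change had nobody started a statin.

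| Start prompted by | Main summary | Initiators excluded |
|---|---|---|
| On-study rise | −1.2 to −10.0 | −1.6 to −5.1 |
| On-study level | −1.5 to −11.5 | −0.8 to −2.6 |
| Nothing related to lipids | −1.0 to −8.8 | about 0 |
| Baseline level only | −1.4 to −11.0 | +0.3 to +1.1 |

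The two analyses err in the same direction in the first two rows only. There the exclusion bias is mostly the smaller one; it is the larger when a rise triggers the start and the statin effect is 20% (for example −1.6 against −1.2).

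**3. Timing of the exclusion.**

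- *E/C/F/TAF.* SAP 8.4.3 stops counting initiation at Week 96. Appendix 7 has no such cut-off: its initiator definition runs to the last E/C/F/TAF dose, and SAP Table 3-2 has a Week 120 fasting window.
- *B/F/TAF.* SAP 8.4.3 covers the whole extension, which Appendix 7 ends at the last B/F/TAF dose. Treatment lasts at least 48 weeks, and SAP Table 3-7 has a Week 60 window. A subject starting a statin after the Week 48 OL sample loses that untreated value. One starting between Weeks 24 and 48 OL loses an untreated Week 24 OL value.

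**4. Behaviour of the remedy.** In a multi-visit check with a true change of +10 and an assumed 30% statin effect, the main summary gave +4.4, exclusion +8.7 and the last value before initiation +10.5. A second multi-visit check put the overstatement from carrying that value forward at +0.4 to +1.3.

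**The case against.** - **The reason for starting is not stated.** This stands, and it makes the direction conditional. Simvastatin and lovastatin are disallowed in the E/C/F/TAF phase (Protocol Table 4-1), so a new record may replace a stopped drug. Cardiovascular disease and diabetes, recorded as baseline history, could be other reasons.
- **Other outputs retain the rise.** Worst-grade summaries include values from before the statin, earlier visits show change before initiation, and initiator counts are planned. This stands in part: these outputs reveal the problem but do not correct the change estimates.
- **The exclusion analysis is usually nearer the truth than the main summary.** This stands. It reduces the problem without removing it, and a summary of never-users is legitimate as description.
- **The effect is small against the noise.** With 55 treated subjects, perhaps 30 might remain (assumed). At SD 25 the standard error is 25/√30 = 4.6, about twice the illustrated 2.4. Lipids are not a named endpoint and no formal test is planned. This limits the importance but does not justify the rule.
- **Interim medians were reassuring.** Protocol 1.2.5 reports no clinically relevant change in median fasting lipids at Weeks 24 and 48 of this trial. Nothing stated there shows that statin initiation was taken into account.

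A reader might infer that both analyses necessarily understate any increase, or that the plan cannot show one. The documents support neither: the first needs on-study lipids to prompt treatment, and the second overlooks the graded and by-visit summaries.

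**Conclusion.** The point holds in a limited form. Both sensitivity analyses exclude on a post-baseline event. If on-study lipids prompt statin initiation, they understate rises in total cholesterol, LDL and triglycerides, in the same direction as the main summary and usually by less. Under the assumed LDL inputs with that trigger, the bias is −0.8 to −5.1 mg/dL. It is about zero if initiation is unrelated to lipids and slightly positive if only the baseline level drives it. The actual size cannot be derived from the documents. The argument does not extend to HDL, which the same analyses include.

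The B/F/TAF timing fault follows from the text alone: untreated Week 24 or Week 48 OL values are discarded because of a later start. A reader might infer the same for statins started after Week 96 on E/C/F/TAF. SAP 8.4.3 does not say so; the risk there is only that the Appendix 7 definition is programmed without the cut-off.

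This is a minor improvement to a secondary safety summary and does not affect the trial's main conclusions.

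**What to change.** 1. Exclude only statin users at the start of each phase.
2. Judge initiation against the date of the sample summarised, separately for Week 96 and for Weeks 24 and 48 OL, so that values measured before initiation are kept.
3. For subjects who start before that visit, use the last fasting value before initiation. Present the result beside the planned never-user summary.
4. Align Appendix 7, item 21, which runs to the last dose in both phases, with these cut-offs.
5. State how many subjects have a carried-forward value, and how many of those have only a baseline value. Initiator counts are already planned.

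The cost is SAP wording and minor programming on data already collected. The downside is that carry-forward is an imputation. It can slightly overstate a rise, because a value that triggers treatment tends to be high partly by chance. The first scheduled post-baseline fasting panel is at Week 24 of each phase, so anyone starting earlier will usually have only baseline to carry, which sets the change to zero. Showing both summaries lets the reader judge each limitation.
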